## 8 Appendix

### 8.1 Imputation rules

#### 8.1.1 Study drug

The following rule should be used for the imputation of the dose end date for a given study treatment component:

**Scenario 1:** If the dose end date is completely missing and there is no EOT page, and no death date, the patient is considered as on-going:

The patient should be treated as on-going and the cut-off date should be used as the dose end date. Scenario 1 should not be applicable for final CSR. All patients should have EOT page complete before the Database lock for Final CSR.

**Scenario 2:** If the dose end date is completely or partially missing and the EOT page is available:

Case 1: The dose end date is completely missing, and the EOT completion date is complete, then this latter date should be used.

Case 2: Only Year(yyyy) of the dose end date is available and yyyy < the year of EOT date:

**Use Dec31yyyy**

Case 3: Only Year(yyyy) of the dose end date is available and yyyy = the year of EOT date:

**Use EOT date**

Case 4: Both Year(yyyy) and Month (mm) are available for dose end date, and yyyy = the year of EOT date and mm < the month of EOT date:

**Use last day of the Month (mm)**

All other cases should be considered as a data issue and the statistician should contact the data manager of the study.

After imputation, compare the imputed date with start date of treatment, if the imputed date is < start date of treatment:

**Use the treatment start date**

Patients with missing start dates are to be considered missing for all study treatment component related calculations and no imputation will be made. If start date is missing then end-date should not be imputed.

### 8.1.1 AE, ConMeds and safety assessment date imputation

**Table 5-1 Imputation of start dates (AE, CM) and assessments (LB, EG, VS)**

Missing Element	Rule
day, month, and year	

• No imputation will be done for completely missing dates

day, month	

• If available year = year of study treatment start date then

○ If stop date contains a full date and stop date is earlier than study treatment start date then set start date = 01JanYYYY

○ Else set start date = study treatment start date.

• If available year > year of study treatment start date then 01JanYYYY

• If available year < year of study treatment start date then 01JulYYYY

Missing Element	Rule
day	

• If available month and year = month and year of study treatment start date then

○ If stop date contains a full date and stop date is earlier than study treatment start date then set start date= 01MONYYYY.

○ Else set start date = study treatment start date.

• If available month and year > month and year of study treatment start date then 01MONYYYY

• If available month and year < month year of study treatment start date then 15MONYYYY

**Table 5-2 Imputation of end dates (AE, CM)**

Missing Element	Rule (* = last treatment date plus 30 days not > (death date, cut-off date, withdrawal of consent date))
day, month, and year	

Completely missing end dates (incl. ongoing events) will be imputed by the end date of the on-treatment period*

day, month	

If partial end date contains year only, set end date = earliest of 31DecYYYY or end date of the on-treatment period *

day	

If partial end date contains month and year, set end date = earliest of last day of the month or end date of the on-treatment period*

Any AEs and ConMeds with partial/missing dates will be displayed as such in the data listings.

Any AEs and ConMeds which are continuing as per data cut-off will be shown as 'ongoing' rather than the end date provided.

The above imputations are only used for analyses of time to and duration of AEs and concomitant medications.

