1 st occurrence and subsequent occurrences	
 Educate subject about pyrexia and its associated syndrome (chills or rigors or night sweats or flue like symptoms) to ensure prompt recognition and reporting Clinical evaluation for infection and hypersensitivity ^b Laboratory work-up ^b Prompt administration of anti-pyretic treatment with non-steroidal anti-inflammatory drugs (NSAID) and/or paracetamol and/or metamizole at the onset of pyrexia ^a or of pyrexia syndrome Recommend oral corticosteroids (i.e., prednisone 10 mg/d) for at least 5 days or as clinically indicated^c Optimize oral corticosteroid dose as clinically indicated for pyrexia that cannot be managed with dose interruptions^c Oral hydration should be encouraged in subjects without evidence of dehydration. Intravenous hydration is recommended in subjects experiencing pyrexia complicated by dehydration/hypotension. 	
 Dabrafenib and trametinib must be interrupted promptly at the very first observation of pyrexia and should be restarted upon resolution of pyrexia (temperature < 38°C) at the same dose if pyrexia free at least 24 hours*. If recurrent pyrexia cannot be managed with interruption or prophylactic steroids, dose reduce as per Table 6-5. Re-escalation of the subject's dose is recommended if criteria in Section 6.5.1.2 are met. Note: proactive intermittent dosing is not allowed.

* Dabrafenib and Trametinib can be interrupted in the presence of pyrexia syndrome (i.e. symptoms without documented temperature ≥ 38°C degrees) at investigator discretion for recurrent pyrexia.

^a Anti-pyretic treatment should be started immediately at the onset of pyrexia or pyrexia syndrome, and prophylactic anti-pyretic treatment is recommended. Anti-pyretic treatment may include acetaminophen, ibuprofen, metamizole, or suitable anti-pyretic medication according to institutional standards. Prophylactic anti-pyretic treatment is recommended to be discontinued after three days in the absence of pyrexia.

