## Data included in the analysis

The analysis cut-off date for the primary analysis will be September 26, 2020. This date will be changed based on whether all enrolled 556 patients will complete 12 months of treatment or will discontinued from the study.

All statistical analysis will be performed using all data collected in the database up to the data cut-off date. All data with an assessment date or event start date (e.g. start date of an adverse event) prior to or on the cut-off date will be included in the analysis. Any data collected beyond the cut-off date will not be included in the analysis and will not be used for any derivations.

All events with start date before or on the cut-off date and end date after the cut-off date will be reported as 'ongoing'. The same rule will be applied to events starting before or on the cut-off date and not having documented end date. This approach applies, in particular, to adverse event and concomitant medication reports. For these events, the end date will not be imputed and therefore will not appear in the listings.

The analysis cut-off date for the final analysis of study data will be established at the end of the study.

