### **On-treatment assessment/event and observation periods**

For adverse event reporting the overall observation period will be divided into three mutually exclusive segments:

1. **pre-treatment period:** from day of patient's sign informed consent to the day before first administration of study treatment.
2. **on-treatment period:** from date of first administration of study treatment to 30 days after date of last actual administration of any study treatment: dabrafenib or trametinib (including start and stop date).
3. **post-treatment period:** starting at day 31 after last administration of study treatment.

For cases where time of assessment and time of treatment start/stop is captured (e.g. ECG's laboratory assessments), the last available assessment before the treatment period start/stop date/time will be used.

If dates are incomplete in a way that clear assignment to pre-, on-, and post-treatment period cannot be made, then the respective data will be assigned to the on-treatment period. Refer to [section 5.1.1](#) for imputation rules concerning AE start and stop dates.

Safety summaries (tables, figures) include only data from the on-treatment period with the exception of baseline data which will also be summarized where appropriate (e.g. change from baseline summaries). In addition, a separate summary for death including on treatment and post treatment deaths will be provided. In particular, summary tables for adverse events (AEs) will summarize only on-treatment events, with a start date during the on-treatment period (**treatment-emergent** AEs).

However, all safety data (including those from the post-treatment period) will be listed and those collected during the pre-treatment and post-treatment period will be flagged.

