### 5.8.1.1 Pyrexia

For pyrexia, other characteristics like number of episodes, duration, and AE management (including concomitant medications and study treatment modifications) due to pyrexia will be summarized..

The number (%) of patients who received medications for treatment of pyrexia will be summarized along with the type of medications.

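### The imputation of a missing fever end date ignores a recorded drug restart, so a short early fever can be analysed as lasting about 346 days

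*SAP*

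**What the plan says.** SAP section 8.1.1, Table 5-2, covers adverse events and concomitant medications alike: "Completely missing end dates (incl. ongoing events) will be imputed by the end date of the on-treatment period". The table defines that date as "last treatment date plus 30 days not > (death date, cut-off date, withdrawal of consent date", which agrees with the on-treatment period in SAP section 5.1.1, running "from date of first administration of study treatment to 30 days after date of last actual administration of any study treatment". Its scope is limited: "The above imputations are only used for analyses of time to and duration of AEs and concomitant medications".

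SAP section 5.1, Data included in the analysis, says of events with no documented end date: "For these events, the end date will not be imputed and therefore will not appear in the listings".

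For pyrexia, Protocol section 6.5.1.1 and Table 6-4 interrupt dabrafenib and trametinib at onset. Both drugs "should be restarted upon resolution of pyrexia (temperature < 38°C) at the same dose if pyrexia free at least 24 hours". Interruptions and dose changes are recorded in the eCRF (Protocol Table 8-1, footnote 6; SAP section 5.4.1).

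Duration of pyrexia is among the other secondary endpoints (Protocol Table 2-1; SAP Table 1-1). SAP section 5.8.1.1 summarises "other characteristics like number of episodes, duration, and AE management". The AESI duration rule in SAP section 2 takes the latest end date minus the earliest start date plus 1 over the records it joins, and does not mention dose restart.

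**The concern.** Carrying an undated event to the end of the observation window is a common default and can suit chronic events. It suits fever in this trial poorly. Fever here is short and recurrent, and Protocol section 4.1 describes it as occurring early in treatment, so the imputed interval will tend to be long. The trial also collects data that bear directly on the missing date. When both drugs are stopped for a fever and dosing later resumes as the protocol describes, the restart date is an approximate upper bound on the end of that fever. Table 5-2 overlooks this and carries the fever through months of recorded dosing.

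At stake is the description of how long fevers last under the adapted algorithm. A few undated records can dominate the mean and set the maximum, and the error makes the algorithm look worse than it is.

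**Working it through.** The plan states no imputed duration, so there is no figure of its own to reproduce. The counting convention can be checked: SAP Table 2-3 counts 25Feb2016 − 01Jan2016 + 1 = 56 days, an inclusive count, and the AESI duration rule also adds 1.

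**Inputs from the documents**
- Imputed end = last dose day L + 30 (SAP Table 5-2). The caps at death, cut-off and consent withdrawal are taken as not binding.
- Full course: up to 12 months, with a study month of 28 days (Protocol section 3), so L = 12 × 28 = 336. A 365-day course is shown as an upper case.

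**Assumptions**
- Onset day, restart day, true length of fever and share of undated episodes are illustrative.

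**Imputed duration** = (L + 30) − onset + 1

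| Onset day | L = 336 (end Day 366) | L = 365 (end Day 395) |
|---|---|---|
| 1 | 366 | 395 |
| 21 | 346 | 375 |
| 30 | 337 | 366 |
| 31 | 336 | 365 |
| 60 | 307 | 336 |
| 180 | 187 | 216 |

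For a fever starting on Day 21 of a 336-day course: 336 + 30 − 21 + 1 = 346 days, or 346 / 336 = 103.0% of the exposure. The imputed fever exceeds the exposure whenever L + 31 − onset > L, that is, for any onset before Day 31.

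**Same fever, bounded by the restart.** If both drugs are interrupted for it and dosing resumes on Day 25, the latest end is Day 24: 24 − 21 + 1 = 4 days, or 4 / 336 = 1.2% of the exposure.

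**Effect on a summary.** Suppose true episodes last 4 days and a fraction f is undated, with imputed length D. The mean is (1 − f) × 4 + f × D.

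| f | D = 187 | D = 346 |
|---|---|---|
| 0.5% | 4.9 | 5.7 |
| 1% | 5.8 | 7.4 |
| 2% | 7.7 | 10.8 |
| 5% | 13.2 | 21.1 |

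The median stays at 4 days throughout; the maximum becomes 187 or 346.

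**The case against.** Several points on the other side stand.

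- **Frequency.** The documents suggest that few fevers will lack an end date: diaries checked at monthly visits (Protocol section 6.6.1), a start and end date or a not-recovered outcome for each event, with follow-up to resolution (section 10.1.1), and queries for missing values (section 11.2). The share is unknown, and the means above rest on assumed shares.
- **Reach.** The primary composite counts subjects with an event, and the imputation is confined to time-to and duration analyses, so the primary result is untouched. Pyrexia duration is descriptive, and SAP section 5.1 also reports the median. The percentage-of-time-in-pyrexia calculation (SAP section 7.2), which could exceed 100% under this rule, belongs to the label-update analyses that SAP sections 2 and 3 drop from the final analysis.
- **Strength of the restart evidence.** Table 6-4 says the drugs should be restarted and covers fever suspected to be treatment-related. The AESI term list (SAP section 5.8.1.2) is wider and includes influenza-like illness. For symptoms without a documented temperature of 38 °C or more, interruption is discretionary. A restart is therefore informative only after a recorded interruption of both drugs for that event.

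Two stronger readings are tempting. A reader might infer that SAP section 5.1 and Table 5-2 contradict each other. They can be read together: the first concerns reporting and listings, while the second imputes for duration and still shows continuing events as ongoing in listings. A reader might also infer that the imputed interval swallows later episodes and lowers the episode count. That would follow only if the occurrence rules in SAP section 2 run on imputed dates. The SAP does not say whether they do, and Table 5-2 confines the imputation to time-to and duration analyses.

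None of this answers the central point: where a restart after a pyrexia interruption is on file, the rule disregards it.

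**Conclusion.** The concern holds as a modest correction to a descriptive secondary summary. As written, Table 5-2 can assign 346 days to a fever starting on Day 21 when the dose records indicate that it ended within days. For a full 336-day course the imputed length runs from 366 days (onset Day 1) to 187 days (onset Day 180). A result near one year needs an early onset, a near-complete course and no binding cap; with a shorter course or a later onset the distortion is smaller.

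The effect falls on the mean and maximum of pyrexia duration. Its size depends on the number of undated records, which the documents do not give. They do not support a claim that the primary conclusion, the median duration or, on present wording, the episode count is distorted.

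**What to change.** Add to Table 5-2 for pyrexia terms with a completely missing end date:

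- Where an interruption of both drugs for that event is recorded at or after onset and dosing then resumes, set the end to the earlier of the current rule and the day before the first non-zero dose after that interruption, and never before the onset date.
- Where there is no such interruption and restart, treat the duration as censored at the end of the on-treatment period, not as complete.

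Both conditions in the first bullet are needed. Dabrafenib is taken twice daily, so a plain cap at the day before the next dose would put the end before onset if the evening dose was taken on the day of onset. It would also force a one-day fever on a subject who never interrupted, shortening durations in favour of the algorithm under test.

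Also state that SAP section 5.1 governs listings and Table 5-2 governs duration derivations, and say whether the occurrence and AESI rules in SAP section 2 use imputed dates.

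The cost is SAP wording and a merge of adverse event and dose records already collected. This is a derivation rule; it changes no instruction on treatment.

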#### **8.1.1.1 Other imputations**

##### **Incomplete date of initial diagnosis of cancer and date of most recent recurrence**

Missing day is defaulted to the 15th of the month and missing month and day is defaulted to 01-Jan.

##### **Incomplete assessment dates for tumor assessment**

All investigation dates (e.g. MRI scan, CT scan) must be completed with day, month and year. If one or more assessment dates are incomplete but other investigation dates are available, this/these incomplete date(s) are not considered for calculation of the assessment date and assessment date is calculated as the latest of all investigation dates (e.g. MRI scan, CT scan) if the overall response at that assessment is CR/PR/SD/UNK. Otherwise – if overall response is progression – the assessment date is calculated as the earliest date of all investigation dates at that evaluation number. If all measurement dates have no day recorded, the 1st of the month is used. If the month is not completed, for any of the investigations, the respective assessment will be considered to be at the date which is exactly between previous and following assessment. If a previous and following assessment is not available, this assessment will not be used for any calculation.

##### **Applying the cut-off to tumor assessment**

For tumor related assessments, if an evaluation has some assessments done prior to cut-off date and others after the cut-off date, then the evaluation is considered post-cut-off date and will be excluded from analysis.

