coverage and prescribed use of contrast. The method of assessment should be noted as CT on the CRF.

Clinical examination: New lesions detected by clinical examination must be biopsied, where possible, to confirm disease recurrence. If a biopsy cannot be obtained then CT/MRI must be done to confirm disease recurrence.

CT and MRI: Contrast enhanced CT with 5mm contiguous slices is recommended. MRI is acceptable (refer to [Section 8.3.1](#)), but when used, the technical specification of the scanning sequences should be optimized for the evaluation of the type of disease.

Whenever possible the same scanner should be used.

Brain Scan: For the baseline brain scan and any post-baseline brain scans, contrast enhanced MRI is preferable to contrast enhanced CT.

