8.3.1.3 Post-baseline imaging assessments

Imaging assessments as described in [Table 8-1](#), [Table 8-2](#), and [Table 8-4](#) should be performed using the same imaging modality used at baseline, irrespective of study treatment interruption or actual dosing. Imaging assessments for response evaluation will be performed according to [Table 8-1](#), [Table 8-2](#), and [Table 8-4](#) until disease relapse, death, lost to follow-up, withdrawal of consent or the 24 month/ EoS assessment. Imaging assessments should be scheduled using Day 1 as the reference date (not the date of the previous tumor assessment), and should be respected regardless of whether treatment with study treatment is temporarily withheld, permanently discontinued, or unscheduled assessments performed.

Tumor assessments after start of new anti-neoplastic therapy post-relapse are recommended however not required. Best response to anti-neoplastic therapy after relapse will be collected on the eCRF.

Additional imaging assessments may be performed at any time during the study at the investigator's discretion to support the efficacy evaluations for a subject, as necessary. Clinical suspicion of disease relapse at any time requires a physical examination and imaging assessments to be performed promptly rather than waiting for the next scheduled imaging assessment.

Combined PET/CT may be used only if the CT is of similar diagnostic quality as a CT performed without PET, including the utilization of IV contrast media. At the discretion of the Investigators, FDG-PET scans may be performed to document relapse.

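### The SAP's tumour-assessment date rules can drop a documented relapse from the descriptive RFS analysis: mainly one with no usable month, and on paper one whose evaluation straddles the cut-off (minor)

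*SAP*

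**What the plan says.** **Incomplete dates (SAP 8.1.1.1, Incomplete assessment dates for tumor assessment).** The section requires full dates and then gives fallbacks.

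- Another investigation in the same evaluation has a date: "If one or more assessment dates are incomplete but other investigation dates are available, this/these incomplete date(s) are not considered", and the evaluation is kept.
- The month is missing: the assessment goes to the midpoint between the previous and following assessments.
- The midpoint cannot be formed: "If a previous and following assessment is not available, this assessment will not be used for any calculation".

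For a progression, "the assessment date is calculated as the earliest date of all investigation dates at that evaluation number"; other evaluations are dated at their latest investigation. I read progression here as recurrence, since this is an adjuvant trial.

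**Cut-off (SAP 8.1.1.1, Applying the cut-off to tumor assessment).** The rule is that "if an evaluation has some assessments done prior to cut-off date and others after the cut-off date, then the evaluation is considered post-cut-off date", and such an evaluation is excluded whatever it shows.

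**General rules.** SAP 5.1 says of "All data with an assessment date or event start date (e.g. start date of an adverse event) prior to or on the cut-off date" that they are in the analysis. SAP 5.7.1 bases RFS on all data observed up to the cut-off.

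**Imaging schedule.** Protocol 8.3.1.3 has scans continue "until disease relapse, death, lost to follow-up, withdrawal of consent or the 24 month/ EoS assessment". Table 8-4 also ends scheduled scans at recurrence or new therapy, and Table 8-3 (post-relapse follow-up) lists none.

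**The concern.** The missing-month fallback relies on a following assessment, and relapse is the outcome after which scheduled scans stop. A recurrence-free scan with a missing month usually has a later scan and can be placed at a midpoint. A relapse with the same defect usually cannot, and is removed. Once new therapy starts, SAP 5.7.3 censors the subject at the last efficacy assessment before it, so a later death does not restore the event. Losses of this kind run in one direction, towards higher RFS.

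The cut-off rule raises a consistency problem. Suppose a scan before the cut-off shows recurrence and a biopsy or further scan in the same evaluation follows after it. The earliest-investigation rule and SAP 5.1 make this an event before the cut-off; the straddle rule excludes it. Two programmers could follow the SAP and classify the subject differently.

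At stake are the 12- and 24-month RFS rates, which are listed secondary endpoints.

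**Working it through.** The documents give no figure for the effect of either rule, so there is none to reproduce. As an anchor, the Wald 95% intervals for the COMBI-AD 12-month RFS rates (88% with n = 435; 56% with n = 432) come out at 84.9-91.1% and 51.3-60.7%. These match the 85-91% and 51-61% in protocol 12.7.

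**Inputs from the documents**
- N = 556 (SAP 4); benchmark 12-month RFS 88% (protocol 12.7).
- Scans at Months 3, 6, 12, 15, 18 and 24 in 28-day months: days 85, 169, 337, 421, 505 and 673.
- SAP analysis months of 30.4375 days: landmarks at days 365.25 and 730.5.
- Primary cut-off 26 September 2020, 12 months after LPFV; final analysis 24 months after LPFV.

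**Assumptions**
- Exponential relapse times.
- 1%, 2% or 5% of relapses have no usable month.
- 7, 14 or 28 days from first to last investigation in an evaluation.
- Accrual fitted to 37 treated by 30 November 2018 and 234 by 12 March 2019, with first dose on 1 September 2018 and LPFV on 26 September 2019.
- Final cut-off on 26 September 2021.

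**Missing month, by hand.** Daily hazard h = -ln(0.88)/365.25 = 0.00035. The last scheduled scans before the landmarks are at days 337 and 673, so the Kaplan-Meier estimates are about exp(-337h) = 0.8887 and exp(-673h) = 0.7901. If a fraction f of relapses is deleted and those subjects are censored at the prior scan, S becomes about S^(1-f).

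| f | 12 months: S^(1-f), gain | 24 months: S^(1-f), gain |
|---|---|---|
| 1% | 0.8898, +0.11 points | 0.7920, +0.19 points |
| 2% | 0.8908, +0.21 points | 0.7939, +0.37 points |
| 5% | 0.8940, +0.53 points | 0.7995, +0.94 points |

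**Missing month, by simulation (600 runs, scans on target days).** Gains were 0.10 / 0.21 / 0.53 points at 12 months and 0.17 / 0.36 / 0.92 points at 24 months. About 117 relapses were observed by the final cut-off, of which 1.1 / 2.3 / 5.8 were dropped. One relapse in 556 is 100/556 = 0.18 points.

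With scans spread over the visit windows (300 runs), the gains were 0.11 / 0.18 / 0.53 points at 12 months and 0.30 / 0.46 / 1.37 points at 24 months. The 24-month figure is less stable there: the last scans scatter around day 673, and subjects scanned early have left the risk set before relapses on later scans are counted.

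**Straddle rule, count at the primary cut-off.** Taking 400 to 500 relapse-free subjects as still assessed (an assumption), expected straddling relapses = number at risk x h x span: 400 x 7 days gives 0.98, 450 x 14 gives 2.2, and 500 x 28 gives 4.9. The simulation with scans on target days gave 22 / 45 / 89 straddling evaluations, of which 0.7 / 1.3 / 2.7 were relapses.

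**Straddle rule, effect.** The comparison is the SAP rule against keeping the relapse at its earliest date.
- 12-month RFS at the primary analysis: 0.00 points with scans on target days; -0.004 to +0.02 points with visit windows. Every subject is about 12 months or more from first dose at that cut-off, so a straddling relapse falls at about month 12 or later.
- 24-month RFS at the final analysis: 0.00 points. The Month 24 scan is at day 673 and the assumed cut-off is at least about 730 days after first dose, so no scheduled scan straddles. If 24 months after LPFV were counted in 28-day months, only the last-enrolled subjects' Month 24 scans could.

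**The case against.** **On the missing month.** Exclusion is a last resort, after any complete date in the evaluation and then a midpoint. Missing values are queried (protocol 11.2). A following assessment can exist: relapse on treatment leads to an EoT visit, with a scan if none was done in the previous 30 days, and tumour assessments after relapse are recommended. No frequency is given, so 1% to 5% is only an assumption. All of this stands and makes the case rare. It does not make the rule right when it is reached, because the text offers a relapse without a following assessment no outcome except removal. The order of the steps is also not fully clear, as the missing-month sentence can be read as triggered by one incomplete date among several.

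**On the cut-off.** The straddle rule ignores outcome and works much like administrative censoring. It can be read as the specific rule that overrides SAP 5.1, and the final analysis re-runs everything, so a relapse that straddled the primary cut-off can be counted then. This largely stands. A reader might infer that relapses straddle more often, since "New lesions detected by clinical examination must be biopsied, where possible, to confirm disease recurrence" and suspected recurrence calls for prompt imaging. That is plausible, but the documents do not say that biopsies and confirmatory scans share the evaluation number of the examination or scan that detected the lesion, and they give no counts.

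**On the remedy.** Keeping straddling recurrences while excluding straddling recurrence-free evaluations could itself look outcome-dependent. But the SAP already dates a recurrence at its earliest investigation and a recurrence-free evaluation at its latest. Applying the cut-off to those dates adds no new asymmetry, and its effect on the landmark rates is about nil.

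**Conclusion.** Minor, and worth correcting. The missing-month fallback is wrong when it is triggered: it normally deletes a documented relapse and can push RFS upward. Under the assumed 1% to 5%, the size is about 0.1 to 0.5 points at 12 months and 0.2 to 0.9 points at 24 months, or up to about 1.4 points at 24 months if scans are spread over the visit windows.

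The straddle rule is a real conflict of wording for a recurrence shown on or before the cut-off. It involves roughly 1 to 5 relapses at the primary cut-off, mostly after month 12 and recoverable at the final re-run. Its expected effect on 12- and 24-month RFS is about nil.

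Two stronger readings are not supported. One is that RFS is overstated as a matter of fact: no counts are available, and the straddle rule moves neither landmark. The other is that every relapse with a missing month is discarded: other dates and the midpoint come first. RFS carries no hypothesis test (SAP 5.7.2), and the primary pyrexia endpoint does not depend on these rules.

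**What to change.** Add two sentences to SAP 8.1.1.1.

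1. A documented recurrence is never dropped for an incomplete date. Use any complete investigation date in the evaluation first. Otherwise impute a date between the last recurrence-free assessment and the next dated record (new anti-cancer therapy, next visit, death or cut-off), consistent with any recorded year.
2. For a recurrence shown on an investigation dated on or before the cut-off, apply the cut-off to the recurrence date given by the earliest-investigation rule, and count it as an RFS event at that date. The whole-evaluation exclusion stays for other straddling evaluations. This brings the section into line with SAP 5.1 and 5.7.1.

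Reporting how many relapses needed an imputed month, and how many evaluations straddled each cut-off, would replace the assumed frequencies with counts. The cost is two sentences and a small change to the RFS derivation before database lock, with no new data.
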